#### **2.1.2 Exclusion Criteria**

- 2.1.2.1 Patients who have received any systemic corticosteroid therapy within 3 weeks prior to the start of therapy with the exception of physiological replacement doses

of cortisone acetate or equivalent.

- 2.1.2.2 Patients who have received any cytotoxic therapy, immunotherapy, antitumor vaccines, monoclonal antibodies or major surgery in the 4 weeks prior to the start of the study.
- 2.1.2.3 Life expectancy of less than 3 months.
- 2.1.2.4 Patients with more than 30% replacement of hepatic parenchyma by tumor or any history of drug related hepatic encephalopathy.
- 2.1.2.5 History of complex ventricular or supraventricular arrhythmias.
- 2.1.2.6 Documented HIV, active bacterial infections, active or chronic hepatitis B, or hepatitis C.
  - A positive hepatitis B serology indicative of previous immunization (i.e., HBsAb positive and HBc Ab negative), or a fully resolved acute hepatitis B infection is not an exclusion criterion.
  - A positive hepatitis C serology is an exclusion criterion.
- 2.1.2.7 Concurrent anticancer therapy (including other investigational agents), with the exception of hormone therapy for prostate cancer (see Section [2.1.1.5](#)).
- 2.1.2.8 Active CNS metastasis (inactive CNS metastasis is defined in Section [2.1.1.11](#)).
- 2.1.2.9 History of severe asthma or presently on chronic inhaled corticosteroid medications (patients with a history of mild asthma controlled with inhaled bronchodilators are eligible).
- 2.1.2.10 History of autoimmune disease, with the exception of an autoimmune event associated with prior ipilimumab (anti-CTLA-4) therapy that has been completely resolved for more than 4 weeks.
- 2.1.2.11 Inability or refusal to practice effective contraception during therapy or the presence of pregnancy or active breastfeeding (men and women of childbearing potential must use an effective method of birth control or abstinence during treatment and for 4 months after completion of treatment).
- 2.1.2.12 Cognitive impairment, history of medical or psychiatric disease, other uncontrolled intercurrent illness, active substance abuse, or social circumstances, which in the view of the Principal Investigator (PI), would preclude safe treatment or the ability to give informed consent.

## **2.2 SCREENING EVALUATION**

Screening evaluation must be performed to determine eligibility within 28 days prior to patient receiving any study intervention, except as indicated below.

- 2.2.1 Complete medical history and physical examination with vital signs and documentation of all measurable or evaluable abnormalities.
- 2.2.2 Computerized tomography (CT) scan of the chest, abdomen, and pelvis. (CT and/or MRI films from outside institution performed within 28 days prior to enrollment may be used to determine eligibility. Same films may be used as baseline if done within 28 days prior to starting treatment.)

- 2.2.3 MRI or contrast-enhanced CT scan of the brain for melanoma subjects or subjects with complaints and/or physical findings suspicious for occult CNS metastasis.
- 2.2.4 Documentation of Karnofsky Performance Score  $\geq 70\%$  or ECOG  $\leq 1$  (see **APPENDIX A**).
- 2.2.5 Verification that the NCI Laboratory of Pathology has confirmed the histology prior to patient registration (No Time Frame). Pathological confirmation of diagnosis can be carried out on available slides from either the primary diagnostic biopsy or subsequent biopsies performed either at the Clinical Center or outside institutions. If necessary, the specimen blocks will be obtained for special stains and other evaluation as deemed necessary to confirm the diagnosis of cancer. If the original pathological material or other diagnostic biopsies are not available, or if there is uncertainty concerning the diagnosis, a repeat biopsy may be undertaken to confirm the diagnosis of cancer.
- 2.2.6 Complete blood count (CBC) with differential and platelet count Acute Care Panel (sodium, potassium, chloride, CO2, glucose, BUN, creatinine); Hepatic panel (alkaline phosphatase, ALT, AST, total and direct bilirubin), LDH, Mineral panel (serum calcium, phosphate, magnesium and albumin) and ammonia level.
- 2.2.7 Serum pregnancy test in women of childbearing potential.
- 2.2.8 Thyroid function tests to include a serum thyroxine (T4) and thyroid-stimulating hormone (TSH).
- 2.2.9 Anti-nuclear antibodies (ANA), rheumatoid factor (RF) and anti-thyroid antibodies
- 2.2.10 Urinalysis.
- 2.2.11 12 lead EKG.
- 2.2.12 Hepatitis B Surface Antigen, Hepatitis B Surface Antibody, Hepatitis B core Antibody and Hepatitis C: HIV 1/2 serology.
- 2.2.13 Pulmonary function tests with DLCO.

### **2.3 REGISTRATION PROCEDURES**

Authorized staff must register an eligible candidate with NCI Central Registration Office (CRO) within 24 hours of signing consent. A registration Eligibility Checklist from the web site (<http://home.ccr.cancer.gov/intra/eligibility/welcome.htm>) must be completed and sent via encrypted email to: NCI Central Registration Office at [[contact]](mailto:[contact]). After confirmation of eligibility at Central Registration Office, CRO staff will call pharmacy to advise them of the acceptance of the subject on the protocol prior to the release of any investigational agents. Verification of Registration will be forwarded electronically via e-mail to the research team. A recorder is available during non-working hours.

### **2.4 BASELINE EVALUATION**

The following tests and procedures will be done within 28 days of initiating treatment with rhIL-15 (except as marked below). If baseline tests were already performed and meet the required time frames, they will not need to be repeated.

- 2.4.1 Baseline history with documentation of sites of disease, physical examination, vital signs and performance score.

- 2.4.2 Serum pregnancy test in women of childbearing potential must be repeated within 3 days prior to starting study drug.
- 2.4.3 CBC with differential, Acute Care Panel, Hepatic Panel, LDH and Mineral Panel must be repeated if not done within 2 weeks of starting study drug.
- 2.4.4 Reticulocyte Count
- 2.4.5 Serum immunoglobulin levels
- 2.4.6 Troponin T or I, based on availability of test in Department of Lab Medicine (DLM)
- 2.4.7 HLA typing (A, B, C, DR, DQ)
- 2.4.8 Serum tumor marker (PSA, CEA, and CA125) assessment if applicable (within 7 days prior to initiating treatment with rhIL-15)
- 2.4.9 CT scan of the chest, abdomen and pelvis, or MRI if CT scan is not sufficient or contraindicated
- 2.4.10 Other imaging studies may be done to document disease as appropriate and at the direction of the PI.
- 2.4.11 Baseline flow cytometry to assess lymphocyte sets and subsets (see Section [5.1.2](#)):
  - 2.4.11.1 One 10-mL lavender-top tubes to Clinical Center Dept. of Lab. Medicine for Lymphocyte Phenotype IL-15 FACS panel.
  - 2.4.11.2 Two lavender-top tubes to the Clinical Support Laboratory in Frederick for special FACS analysis.
- 2.4.12 One 4-mL Serum Separator Tube (SST) tube to the Clinical Support Laboratory in Frederick for inflammatory marker and cytokine analysis (see Section [5.1.3](#)).
- 2.4.13 Optional Tumor Biopsy (see Section [5.1.5](#))

### **3 STUDY IMPLEMENTATION**

#### **3.1 STUDY DESIGN**

This is a Phase I open-label, non-randomized, dose-escalation safety trial of CIV rhIL-15 that will enroll 41 to 47 evaluable patients with metastatic unresectable cancers for which curative or palliative measures either do not exist or are not associated with a survival advantage.

Patients will receive CIV rhIL-15 for 10 consecutive days (240 hours) and will be assigned to a dose level sequentially based on their order of entry into the study. The starting dose will be 0.1 mcg/kg/day and in the absence of significant toxicities, dose escalation will proceed to evaluate dose levels of 0.25, 0.5, 1, 2 and 4 mcg/kg/day. Cycles 1 and 2 will be 42 days in length, but all subsequent treatment cycles will be 28 days in length with an additional 7 days on either schedule allowed for reasons other than recovery for treatment-related toxicities. Subjects will have to demonstrate an absence of anti-IL-15 antibodies in their post-treatment (day 12 and week 4) assessments before additional cycles of rhIL-15 can be initiated.

Radiologic reassessments for 10-day treatment cycle patients will be performed during week 4 (days 26 to 35) of Cycles 1 and 2 and at off-treatment and off-study visits.

After treatment of patients in the expansion cohort for the 10-day schedule is completed, new cohorts of 3 to 6 patients each will begin treatment with the 5-day (120 hour) schedule at dose levels of 3, 4 or 5 mcg/kg/day to define the MTD for this shorter CIV rhIL-15 regimen. All treatment cycles for these cohorts will be 21 days in length.

As of April 2016, twenty-four evaluable patients have enrolled on Dose Levels 1-6; with 2 more to be enrolled in Dose Level 6 after Amendment G. When the study is re-opened for enrollment, an additional 17-23 evaluable patients will be enrolled.

A total of 9 patients will potentially be treated at the MTD or maximum administered dose for both schedules to better characterize the clinical activity of CIV rhIL-15 in this patient population.

Radiologic reassessments for both the 10day and 5-day dosing cohorts will be performed after every other cycle (2, 4, 6, 8 etc.) including the subjects that go onto to receive additional cycles of treatment.

Patients receiving the 10-day treatment schedule without evidence of an ongoing response after any 2 consecutive cycles of treatment will discontinue rhIL-15 and be followed until disease progression is documented or they go off study for another reason. (Ongoing response is defined as: > 15% decrease in sum of marker lesions and/or improvement or disappearance of some non-measurable lesions and/or > 10% decrease in tumor markers.) Patients receiving the 5-day treatment schedule will have 4 cycles of treatment to demonstrate responsiveness to rhIL-15, so that patients are given an equal number of rhIL-15 doses to confirm the treatment has sufficient activity to justify more prolonged treatment.

Patients who demonstrate a complete response (CR) to treatment will receive 2 additional cycles after the cycle where the CR is first documented.

Patients whose best response after 2 consecutive cycles of treatment is stable disease and those who stop treatment due to toxicity will be followed with routine exams and restaging x-rays (every 60 days x 3 and then quarterly) unless progressive disease is documented or they begin another treatment for their cancer.

### **3.2 DOSE-LIMITING TOXICITY**

There are some well-described, clinically inconsequential side effects associated with immunotherapy that are addressed differently than with other types of cancer therapies and affect the consideration of DLTs. Patients receiving rh cytokines often have an initial decrease in their total white blood cell (WBC) counts, significant lymphopenia and occasionally some degree of neutropenia early in the course of their treatment ([66](#), [67](#)). Unlike cytopenias noted in patients receiving cytotoxic chemotherapies, these drops are usually transient and presumed to be related to increased margination (adherence to blood vessel endothelium) or alterations in trafficking that reduces the number of circulating cells rather than the destruction of the mature effector and bone marrow precursor cells ([68](#)). The impediment to normal trafficking (chemotaxis) of various classes of leucocytes best described for patients treated with HD IL-2 marginally increases the risk for infections, especially central catheter-associated bacteremia; but the rate of infections in cytokine-treated patients is substantially less than leucopenic and neutropenic chemotherapy-treated patients ([69](#)).

As such, rh cytokine treatment resulting in grade 3 or 4 cytopenias, especially lymphopenia, in the absence of signs of infection is usually not interrupted. Less commonly, patients receiving

activated T-cells and cytokine therapy will have a significant leukocytosis ([67](#)). Even though these cells are activated and generally large lymphocytes, toxicities seen in leukemic patients with elevated WBC counts are not encountered and therapy is not interrupted based purely on an arbitrary WBC number. In the completed IVB trial and in this protocol, we have observed most commonly during the first 7 days of treatment transient increases in liver function tests (alkaline phosphatase, alanine aminotransferase [ALT] and aspartate aminotransferase [AST] which usually begin to improve while the subject continues treatment and have not been associated with any clinical signs of hepatotoxicity. During the IVB trial, treatment was discontinued for grade 3 elevations ( $> 5$  times ULN) of AST and/ALT in 2 subjects treated at the 1 mcg/kg dose level who otherwise were tolerating their treatment very well. Some subjects previously treated in this protocol have had less significant elevations that have also resolved without incident, DLTs or clinical sequelae. HDIL-2 subjects commonly have abnormalities of their LFTs in many occasions much more abnormal than we have observed in the rhIL-15 subjects and continue their treatment ([59](#), [60](#)). Similar transient increases which resolve spontaneously most often with continued rhIL-15 or in all cases after treatment is stopped have also not been associated clinical hepatotoxicity with the one exception discussed in Section [1.2.1.6](#). We believe that the clinical experience with rhIL-15 in all three trials with the additional limitation on degree of hepatic tumor replacement allows continuation of the DLT exception with regards to ALT, AST, alkaline phosphatase, total and direct bilirubin.

### 3.2.1 DLT will be defined as follows:

Grade 2 diarrhea lasting more than 24 hours or any grade 3 or 4 toxicity, if deemed possibly, probably or definitely related to the study drug by the PI during the first cycle of treatment, **with the following exceptions:**

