### **3.3 DOSE ESCALATION**

Dose escalation will proceed in cohorts of 3 to 6 patients. Patients will not begin treatment at the next higher dose level until all patients treated at the previous dose level have reached day 21 of the protocol, recovered from any clinical or laboratory toxicities and would be able to initiate another cycle of treatment unless restaging has demonstrated progression of their disease). The MTD is the dose level at which no more than 1 of up to 6 patients experience DLT, and the dose below that at which at least 2 (of  $\leq$  6) patients have DLT as a result of the drug. If a patient did not experience DLT and did not finish 1 cycle of treatment (42 days), he or she will not be evaluable for determination of the MTD and will be replaced in the dose level.

Dose escalation will follow the rules outlined in the Table below.

Number of Patients with DLT at a Given Dose Level	Escalation Decision Rule
0 out of 3	Enter up to 3 patients at the next dose level
$\geq 2$	Dose escalation will be stopped. This dose level will be declared the maximally administered dose (highest dose administered). Up to 3 additional patients will be entered at the next lowest dose level if only 3 patients were treated previously at that dose.
1 out of 3	Enter up to 3 more patients at this dose level. 

• If 0 of these 3 patients experience DLT, proceed to the next dose level.

• If 1 or more of this group suffer DLT, then dose escalation is stopped, and this dose is declared the maximally administered dose. Up to 3 additional patients will be entered at the next lowest dose level if only 3 patients were treated previously at that dose.

$\leq 1$ out of 6 at highest dose level below the maximally administered dose	This is the MTD and is generally the recommended phase 2 dose. At least 6 patients must be entered at the recommended phase 2 dose.

The MTD has already been defined for patients treated with the 10-day regimen. For patients treated with the 5-day regimen dose escalation will continue through the 5 mcg/kg/day dose level in the absence of  $\geq 2$  DLTs for the patients treated for any of the dose levels being evaluated for the 5-day regimen. If an MTD is not identified up to 9 patients may be treated at the maximum administered dose (MAD) of 5 mcg/kg/day to better evaluate the therapeutic potential of rhIL-15 given by this schedule.

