#### 7.2.2 NCI-IRB Requirements for PI Reporting at Continuing Review

The protocol PI will report to the NCI-IRB:

1. A summary of all protocol deviations in a tabular format to include the date the deviation occurred, a brief description of the deviation and any corrective action.
2. A summary of any instances of non-compliance
3. A tabular summary of the following adverse events:
  - All Grade 2 **unexpected** events that are possibly, probably or definitely related to the research;
  - All Grade 3 and 4 events that are possibly, probably or definitely related to the research;
  - All Grade 5 events regardless of attribution;
  - All Serious Events regardless of attribution.

**NOTE:** Grade 1 events are not required to be reported.

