The MTD for each schedule will be based on the assessment of DLT during the first cycle of treatment, and will be defined as the dose level at which less than one-third of patients (0/3 or 0-1/6 patients) treated at that dose experience a DLT, with the next higher dose level demonstrating a one-third or greater number of patients ( $\geq 2/3$  or  $\geq 2/6$  patients) having DLT. If a patient did not experience DLT and did not finish 1 cycle of treatment (either 42 or 21 days), he or she will not be evaluable for determination of the MTD and will be replaced in the dose level. An additional 3 to 6 patients will be enrolled at the MTD or, if no severe or dose-limiting toxicities are encountered, the maximum administered dose of rhIL-15, so that a total of 9 patients will potentially be treated at MTD for either schedule to better characterize the clinical activity of

CIV rhIL-15 in this patient population. If feasible, the patients enrolled in this expansion cohort will be limited to histologic cancer subtypes previously shown to be sensitive to immunotherapy (renal cell carcinoma, melanoma, prostate, colorectal and ovarian cancer).

As of April 2016, twenty-four evaluable patients have enrolled on Dose Levels 1-6; with 2 more to be enrolled in Dose Level 6 after Amendment G. A maximum of 6 evaluable patients may be enrolled at DL 7 & 8 with an additional 9 at DL 9. If all dose levels are evaluated (with 6 patients per remaining dose levels and 9 total patients at the MTD or maximum administered dose), a maximum of 47 evaluable patients will be enrolled. An additional 5 patients may be enrolled to compensate for inevaluable patients; thus, bringing the maximum accrual ceiling to 52.

Similarly, if all dose levels are evaluated, the minimum number of patients required will be 41 (24 evaluable patients have enrolled at DL 1-6; with 2 more to be enrolled in Dose Level 6 after Amendment G and with 3 patients enrolled at DL 7 & 8; 9 at DL 9; and 5 inevaluable patients a minimum of 46 will be reached).

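### A drug-related death in cycle 1 is not a DLT as written, so the patient is replaced and drops out of the MTD count

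*Combined protocol and SAP*

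**What the plan says.** Section 3.2.1 has two routes to a DLT. The first is grade 2 diarrhea persisting beyond 24 hours. The second is "any grade 3 or 4 toxicity, if deemed possibly, probably or definitely related to the study drug by the PI during the first cycle". The hematologic and non-hematologic exceptions that follow only remove events from that set. Neither they nor any other section supplied classes a related death as a DLT.

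The replacement rule appears twice. Section 3.3: "If a patient did not experience DLT and did not finish 1 cycle of treatment (42 days), he or she will not be evaluable". Section 8 covers both schedules: a patient without DLT who "did not finish 1 cycle of treatment (either 42 or 21 days), he or she will not be evaluable for determination of the MTD". Both replace the patient, and neither excepts a drug-related death. Section 3.10.2 lists death as an off-study criterion, so a patient who dies in cycle 1 has not finished it.

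The counts then drive these decisions:

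- At 1 of 3, Section 3.3 says "Enter up to 3 more patients at this dose level".
- At 2 or more DLTs, escalation stops. "Up to 3 additional patients will be entered at the next lowest dose level if only 3 patients were treated previously at that dose".
- At no more than 1 of 6 on the highest level below the stopped one: "This is the MTD and is generally the recommended phase 2 dose".
- Section 8 classes 0/3 or 0–1/6 as acceptable, and at least 2/3 or 2/6 as too toxic.

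Before the next higher level opens, Section 3.3 also requires that "all patients treated at the previous dose level have reached day 21 of the protocol, recovered from any clinical or laboratory toxicities". The Schema says that the 10-day MTD has been identified and the 5-day MTD has not.

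**The concern.** A fatal related toxicity is the worst outcome that the DLT rule should register. As written, it is the one grade of related toxicity that the rule does not count. The patient is treated as missing information and replaced by someone who may have no event.

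What is at stake is the declared MTD of the 5-day schedule. The clearest route is back-fill. Suppose a 5-day level first gave 0/3, the level above stopped with two or more DLTs, and three patients are added at the lower level. Among the added patients there is one DLT and one related death without an earlier countable event, and the replacement has no DLT. The written count is 1/6, and Section 3.3 declares that level the MTD. With the death counted it is 2/6, so the level is above the MTD. The MTD then lies at least one level lower, or below the tested 5-day range if this was the lowest level.

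At the top 5-day level, the same counts separate an MTD that was not reached from a level above the MTD.

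**Working it through.** **The plan's own figures.** Section 8 tabulates the probability of escalating for true DLT rates p of 10% to 60%. Under the 3+3 rule it is

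(1−p)³ + 3p(1−p)² × (1−p)³

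| p | 10% | 20% | 30% | 40% | 50% | 60% |
|---|---|---|---|---|---|---|
| Computed | .9061 | .7086 | .4943 | .3093 | .1719 | .0824 |
| Section 8 | .91 | .71 | .49 | .31 | .17 | .08 |

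All six agree, so the rule analysed here is the plan's rule.

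**Set-up.** Take a batch of three containing one related death with no earlier countable event. Let k be the number of DLTs in the two other patients and r (0 or 1) the DLT status of the replacement. The written count for the batch is k + r. With the death counted and no replacement it is 1 + k. Patients are assumed independent, each with countable-DLT rate p.

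**Death in the first three.** The written count is 1/3 and the corrected count 2/3 only when k = 1 and r = 0. Probability: 2p(1−p) × (1−p) = 2p(1−p)².

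**Death in a back-fill batch after 0/3.** The written total is at most 1/6 and the corrected total at least 2/6 only when k = 1 and r = 0. The probability is the same.

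**Death in the second batch at the top 5-day level, after 1/3.** The corrected total is 2 + k, always at least 2/6. The written total is 1 + k + r, which is 1/6 only when k = 0 and r = 0. Probability: (1−p)³.

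| p | 10% | 20% | 30% | 40% | 50% | 60% |
|---|---|---|---|---|---|---|
| First three, or back-fill: 2p(1−p)² | .162 | .256 | .294 | .288 | .250 | .192 |
| Second batch at top level: (1−p)³ | .729 | .512 | .343 | .216 | .125 | .064 |

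These probabilities are conditional on such a death having occurred.

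**Where nothing changes.** If the replacement has a DLT in the first-three or back-fill case, the class is the same either way. With no other DLT among six, 0/6 and 1/6 are both acceptable. With two or more other DLTs the level is too toxic in either count.

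**Not claimed.** With no other DLT in the first three, the counts are 0/3 and 1/3. At a level below the top, before escalation has stopped, they can be 1/6 and 2/6. In both situations the day-21 condition, read literally, already blocks the next level, because a deceased patient cannot meet it.

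**The case against.** **Most fatal toxicities would already count.** Section 3.2.1 does not refer to maximum grade, so a death preceded by a related, non-excepted grade 3 or 4 event is a DLT. Infusion is inpatient with frequent monitoring, and the main exceptions lapse when there are clinical signs. This stands, and it makes the trigger narrow: in essence an abrupt related death. It does not make it empty. In the macaque continuous-infusion study (Section 1.2.1.3), one animal died early in its second course with no significant toxicity seen beforehand and no cause established. That gives no human rate, but it shows the pattern.

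**The percentages are conditional on an event of unknown frequency.** This also stands. Purely as illustration, assume a rate f of such deaths between 1% and 10% per patient, and p = 20% among the others.

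- First or back-fill batch, given that the batch is enrolled: 3f(1−f)³ × 2p(1−p)² = 0.7% to 5.6%.
- Second-batch route at the top level, including reaching 1/3: (1−f)³ × 3p(1−p)² × 3f(1−f)³ × (1−p)³ = 0.6% to 3.1%.

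**Other safeguards exist.** The day-21 condition holds back the next higher level. Section 7.4.1 lets the team base enrolment and escalation on toxicity data. Section 8 allows expansion at the maximum administered dose only without severe or dose-limiting toxicity, and the Schema also requires a confirmed response for 5-day expansion. Deaths are reported and stay in the toxicity data. So the count alone does not decide expansion. But none of these provisions makes the death a DLT or returns the patient to the MTD denominator. The day-21 condition does not apply to back-fill, because escalation has already stopped.

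**The authors surely meant to count such deaths.** Probably so. Section 7.2.2 does list "All Grade 5 events regardless of attribution" apart from grades 3 and 4, but that item has a different attribution rule and would need its own line anyway, so it is weak evidence of intent. The point rests on the literal text of Sections 3.2.1, 3.3 and 8, where the replacement rule points the other way.

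**Conclusion.** The concern holds on the text as written. This is an omission in Section 3.2.1 that the replacement rule turns into a wrong count on a primary objective. For one such death, exactly one other DLT and a DLT-free replacement, 2/3 becomes 1/3 and 2/6 becomes 1/6. Through back-fill this can place the declared 5-day MTD too high.

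Given such a death, the class changes with probability 16–29% in a first or back-fill batch, and 73% falling to 6% in the second batch at the top level. This assumes independent patients and Section 8's own grid of DLT rates. How often such a death would occur cannot be derived from the documents. The 10-day MTD is already declared, so going forward the point concerns the 5-day cohorts. It should be fixed because the rule fails on the most serious outcome and the repair is small.

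**What to change.** Bring the three sections into line on how the event is counted:

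1. In Section 3.2.1, state that a grade 5 event in cycle 1 at least possibly related to study drug counts as a DLT for the MTD determination.
2. In Section 3.3, state that such a patient is evaluable for the MTD and is not replaced.
3. Say the same in Section 8.

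The first change would suffice in logic, since replacement applies only to patients without a DLT; the other two remove doubt. The rest of the replacement rule can stay.

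The cost is wording only: no extra data, assessments or planned patients. The range of 41 to 47 evaluable patients, the ceiling of 52 and the escalation table stand, with the table's true rate read as including related deaths. The DLT count can only become slightly less favourable.
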